13.5 Secondary Objectives

For the secondary objectives, we will determine whether skin toxicity is present when erlotinib is administered weekly at 600 mg for weekly for 3 doses. We will determine if there is a difference in EGFR phosphorylation in neoplastic bladder epithelium 9-18 hours post-study dose between subjects randomized to erlotinib weekly versus placebo. We will assess erlotinib plasma concentrations in subjects taking erlotinib weekly. We will test for differences between arms in expression of phosphorylated ERK in normal and abnormal urothelium. We will examine limited pharmacokinetics of weekly erlotinib. We will determine, for normal, neoplastic tissue, and the difference between normal and neoplastic tissue, if there is a difference in the following markers of EGFR: e-cadherin, Ki-67 and p-ERK, p53, and let-7 micro RNA.

For secondary objectives, all measurements and changes in measurements of interest will be summarized by treatment arm (and, if applicable, by visit) with appropriate descriptive statistics. Compliance, in terms of the number of pills missed, will be summarized by treatment arm with descriptive statistics, and tested for imbalance using Wilcoxon rank-sum test. Patient toxicity throughout the study will be summarized in several ways; the presence or absence of any toxicity, worst CTCAE grade, and strongest investigator-defined relationship will all be examined and characterized by treatment arm, and analyzed appropriately (Wilcoxon rank-sum for ordinal data, Fisher's exact test for dichotomous data, and log rank test for time to event data). For tissue biomarkers, we will examine the differences between the groups for biomarkers in normal and neoplastic tissue, and the difference between normal and neoplastic tissue at the time of surgery; (also, for those with available paired tissue samples we will examine pre to post change) with the appropriate tests; for dichotomous data we will use Fisher's exact test, for ordinal data we will use Wilcoxon rank-sum test, and for continuous data, and a two-sample t-test with normalizing transformation if necessary or Wilcoxon rank-sum test.

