In general, 30%–80% of people with superficial bladder cancer will develop recurrent tumors (Bono 1994). A higher risk of tumor recurrence is associated with multifocal disease observed at the time of initial diagnosis, high tumor grade, depth of invasion, and cystoscopic findings 3 months after diagnosis. It has been reported that 70% of patients with multiple bladder tumors will have recurrent disease by one year, whereas approximately 50% of patients diagnosed with a solitary bladder tumor will experience disease recurrence by 4 years. Up to 10% of recurrent bladder tumors progress to muscle-invasive disease. The risk of tumor progression is lowest for individuals with stage Ta papillary tumors in that only 4% of individuals with Ta tumors will progress to muscle-invasive disease as compared with a 30% progression rate for T1 tumors within 3 years (Grossman 1996).

Bladder cancer is thought to evolve along one of two phenotypic pathways: superficial (papillary) or invasive (Koss 1992). These pathways are characterized by specific genetic defects. The

superficial/papillary pathway genotype is characterized by alterations in chromosome alleles 9p and 9q, while the CIS/invasive pathway is characterized by dysfunction of p53 or pRb (Dalbagni 1993; Rosin 1995; Spruck 1994; Wagner 1995). It is unlikely that these specific genetic derangements alone are sufficient to trigger malignant transformation of normal cells, suggesting that other genetic events or environmental exposure may contribute to their malignant potential as well.

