
2.3 Rationale

The strategy of targeting specific PTKs such as EGFR seems plausible due to the redundancy of growth factor networks and EGFR is overexpressed in a subset of cancers (bladder, breast, cervix, colon, esophagus, lung, prostate, and head and neck). The development of novel therapies remains an area of unmet need in the treatment of both superficial and muscle invasive bladder cancer. One of the most important targets for chemo-preventive intervention and drug development are deregulated signal transduction pathways (Kelloff 1996). Key components of these pathways are the protein tyrosine kinases (PTKs), which catalyze the transfer of the γ -phosphate of ATP to the hydroxyl group of tyrosine on numerous proteins (Chang 1992). Loss of PTK regulatory mechanism has been implicated in neoplastic growth and numerous oncogene codes for PTKs (Powis 1994, Powis and Workman 1994). The strategy of targeting specific PTKs such as EGFR seems plausible due to the redundancy of growth factor networks and EGFR is overexpressed in a subset of cancers (bladder, breast, cervix, colon, esophagus, lung, prostate, and head and neck).

In bladder cancer, EGFR/ERBB2 is frequently overexpressed (> 75% of transitional cell carcinomas) and the level of overexpression has been directly correlated with tumor grade/stage, tumor recurrence and overall survival (Neal 1990, Messing 1990, Mellon 1995, Chow 2001). Experimental evidence in bladder

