7.2 Baseline Testing/Prestudy Evaluation

Baseline Evaluations

Baseline evaluations determine if the participant is a fit candidate for study participation and establish the participant's health status before entering the study. Standard-of-care labs or procedures done prior to signing consent will qualify for these baseline evaluations (i.e. physical exams, routine labs, vital signs) provided they were obtained within 30 days of the participant's Day 1 dose of study agent. All baseline evaluations (including labs) must be completed before requesting randomization and dispensing study drug. An Eligibility Checklist will be provided by the CLO at study initiation to help determine if the participant is eligible for the trial. This document will need to be signed and submitted to the CLO at the time of randomization.

Baseline **cystoscopy** demonstrating a bladder tumor. The physician should assess if the bladder tumor is invasive or non-invasive. The baseline cystoscopy must be completed within 120 days of randomization.

At the screening/baseline visit, blood for pharmacokinetics may be collected before eligibility has been confirmed. However, if the participant is later found to be ineligible, the sample may not be used. If the participant is found to be ineligible, clearly document the destruction of the pharmacokinetic blood sample in the participant's research chart.

A review of the participant's **medical history** will be done within 30 days of randomization.

A **physical examination** must be performed within 30 days of randomization.

Performance Status, using the Karnofsky must be assessed

A review of **concomitant medications** will be done within 30 days of randomization.

Laboratory tests needed for eligibility are: WBC, platelets, hemoglobin, total bilirubin, AST, ALT, alkaline phosphatase, creatinine, sodium and potassium. All of these laboratory analyses must be completed within 30 days before randomization.

Women of child-bearing potential must have a negative pregnancy test within 30 days of randomization.

Plasma Pharmacokinetics - Levels of erlotinib and metabolites will be assessed for all participants.

International Prostate Symptom Score (I-PSS) – The participant will complete the survey within 30 days of randomization

Review of Study Participation and Study Calendar - The research staff should review the upcoming

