9. CORRELATIVE/SPECIAL STUDIES

9.1 Rationale for Methodology Selection

Erlotinib Pharmacokinetics. Pharmacokinetic parameters have been consistently associated with erlotinib toxicity, an important consideration in chemoprevention trials and will be assessed as part of this trial. (White, 2011, Lu 2006)

Blood samples will be collected prior to starting therapy, prior to dosing on day 8 (if available), and on the day of surgery, approximately day 16. Erlotinib and its principal metabolite OSI-420 will be evaluated by high-performance liquid chromatography as previously described (Hamilton 2006).

EGF receptor. EGF receptor (EGFR) is upregulated in most epithelial cancers where signaling through EGFR contributes to cancer cell proliferation and survival. The limited clinical efficacy of EGFR inhibitors suggests that identification of resistance mechanisms may identify new pathways for therapeutic targeting. E-Cadherin. Studies have shown that the extent of loss of E-cadherin was associated with the depth of urothelial carcinoma invasion (Sun 2002), and that E-cadherin plays a central role in modulation of EGFR response in urothelial carcinoma (Black 2008). Ki67. Antigen KI-67 is a nuclear protein that is associated with and may be necessary for cellular proliferation. Lubet et al. (Lubet 2013 submitted) observed decreased Ki67 expression in response to weekly erlotinib in the MNU mouse breast cancer model as well as a significant decrease in phosphorylated ERK expression. ERK. Extracellular regulated kinase (ERK) is an important downstream factor of EGFR in MAP kinase pathway. Its activation (phosphorylation) plays a key role in carcinogenesis and cancer progression of many cancers (Lujan 2010, Chou 2010) including urothelial carcinoma (Lee 2013, Ling 2011). Study showed that aberrant ERK activation causes resistance to some EGFR kinase inhibitors (Ercan 2012).

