13.3 Sample Size and Feasibility

The sample size for each group is based on comparing EGFR phosphorylation in bladder epithelium as measured by quantitative Vectra assay analysis of expression between the erlotinib and placebo arms. This primary endpoint can be considered a continuous random variable. The sample size justification is thus based on a two-tailed two-sample t-test of the difference between the two groups at a significance level of 0.05. In order to detect an effect size of 1, i.e. the difference in the mean change between the placebo arm and the erlotinib arm of 1 standard deviation, with power 0.85, the trial requires an effective sample size of 14 in the placebo arm and 28 in the erlotinib arm. Assuming a random drop-out of up to 5%, 15 subjects in the placebo arm and 30 subjects in the erlotinib arm will be enrolled for a total of 45 subjects for this exploratory study.

There will be six sites participating in the study. Each randomized patient will be treated with study medication weekly x 3 doses. We will allow for study duration of approximately 3 years.

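### The tumor-tissue marker comparisons in Section 13.5 use neither the baseline invasive/non-invasive assessment nor the planned-surgery stratum, which costs precision for the markers that the protocol links to invasion or stage

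*Combined protocol and SAP*

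**What the plan says.** Section 13.5 covers phosphorylated EGFR, E-cadherin, Ki-67, p-ERK, p53 and let-7. It states that "we will examine the differences between the groups for biomarkers in normal and neoplastic tissue", and likewise for the difference between the two tissues, with pre-to-post change where paired samples exist. The tests are Fisher's exact, Wilcoxon rank-sum or a two-sample t-test, depending on data type. No covariate or stratified test is named. The only covariates in Section 13 (dose received, smoking and proton pump inhibitor use) belong to the supporting analysis of the primary endpoint in Section 13.4.

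Section 4.1.1 admits both invasive and non-invasive tumors. At the baseline cystoscopy, Section 7.2 says, "The physician should assess if the bladder tumor is invasive or non-invasive". Section 13 does not mention this assessment. Section 13.2 stratifies randomization by planned surgery (TURBT or cystectomy), but the tumor-tissue analysis does not use that factor either.

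On what the markers are expected to track:
- **EGFR/ERBB2 expression:** "the level of overexpression has been directly correlated with tumor grade/stage" (Section 2.3).
- **E-cadherin:** "the extent of loss of E-cadherin was associated with the depth of urothelial carcinoma invasion" (Section 9.1).
- **p53:** "the CIS/invasive pathway is characterized by dysfunction of p53 or pRb" (Section 2.1).

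**The concern.** If tumor type explains part of the spread of a marker, an unadjusted two-sample test leaves that part in its error term. With few participants, the arms can also differ by chance in their invasive share, which moves the observed contrast in either direction. The number of tumor samples is uncertain, because Section 1.2 assesses phosphorylated EGFR in tumor only where tissue is available; 15 v 30 is therefore a ceiling. A covariate that the protocol already asks for before dosing could recover some precision, and prespecifying it would avoid choosing one after the data are seen.

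**Working it through.** **The plan's own figure.** Section 13.3 assumes a "two-tailed two-sample t-test of the difference between the two groups at a significance level of 0.05", an effect size of 1 SD and 1:2 allocation, and states that "with power 0.85, the trial requires an effective sample size of 14 in the placebo arm and 28 in the erlotinib arm". By the normal approximation, placebo n = (1.960 + 1.036)² × (1 + 1/2) = 13.5, rounded up to 14, with 28 on erlotinib. Noncentral-t power at 14 v 28 is 0.846. Dividing by 0.95 for 5% drop-out gives 15 and 30. The figures reproduce. They concern the primary endpoint in normal-appearing urothelium; no effect size or power is stated for tumor tissue.

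**Precision.** Inputs: n = 15 v 30 (Section 13.3); p = invasive share; D = difference between invasive and non-invasive tumors in within-type SDs. Neither p nor D is given for this trial. Section 2.1 puts muscle-invasive disease at up to 30% of initial diagnoses, used here as the upper value. A lower value of 10% is assumed because the trial also takes recurrent tumors and restricts muscle-invasive entry (Section 4.1.1.1).

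R² = p(1−p)D² / (1 + p(1−p)D²). Standard-error reduction = 1 − √(1−R²). Sample-size equivalent = 1/(1−R²).

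| p | D | R² | SE reduction | Equivalent extra participants |
|---|---|---|---|---|
| 0.10 | 0.5 | 0.02 | 1% | 2% |
| 0.10 | 1.0 | 0.08 | 4% | 9% |
| 0.10 | 1.5 | 0.17 | 9% | 20% |
| 0.30 | 0.5 | 0.05 | 3% | 5% |
| 0.30 | 1.0 | 0.17 | 9% | 21% |
| 0.30 | 1.5 | 0.32 | 18% | 47% |

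These are before the cost of estimating one coefficient. At N = 45 under simple randomization that inflates the variance by about 1/(N−4) = 1/41 = 2.4%, or 1.2% in the standard error. The first row is therefore break-even.

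**Power over a range of R²** (noncentral t, 1 SD effect on the total-SD scale, one fewer degree of freedom when adjusted; 10 v 20 with tumor tissue is an assumption):

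| R² | 15 v 30 | Detectable at 85% power, 15 v 30 | 10 v 20 |
|---|---|---|---|
| unadjusted | 0.871 | 0.97 SD | 0.703 |
| 0.1 | 0.903 | 0.92 SD | 0.747 |
| 0.2 | 0.932 | 0.87 SD | 0.795 |
| 0.3 | 0.958 | 0.81 SD | 0.845 |
| 0.4 | 0.979 | 0.75 SD | 0.895 |

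At R² = 0 the detectable difference at 15 v 30 is 0.970 SD adjusted and 0.969 SD unadjusted.

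**Chance imbalance.** Under simple randomization with p = 0.30, the SD of the between-arm difference in invasive share is √(0.3 × 0.7 × (1/15 + 1/30)) = 0.145. A gap of 20 points or more is 0.20/0.145 = 1.38 SDs, a two-sided probability of 17%. With p = 0.10 the SD is √(0.09 × 0.1) = 0.095 and the probability 3.5%.

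The trial stratifies by planned surgery, so permuted blocks of 3 were simulated within both stratification factors at p = 0.30:

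| Cystectomy planned for | P(gap of 20 points or more) |
|---|---|
| surgery uninformative about invasion | 18% |
| 50% of invasive, 5% of non-invasive tumors | 12% |
| 80% of invasive, 5% of non-invasive tumors | 4% |
| all invasive, no non-invasive tumors | about 0% |

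**The two effects are one quantity.** On the within-type SD scale the adjusted standard error is √(1/15 + 1/30) = 0.316. With p = 0.30 and D = 1 the unadjusted one is √1.21 × 0.316 = 0.348. Its variance, 0.121, is 0.100 plus the imbalance variance 0.145² = 0.021. A 20-point gap at D = 1 shifts the contrast by 0.20, against the unadjusted standard error of 0.348.

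**The case against.** The strongest defence is that unadjusted two-sample tests are valid under randomization, that the study is declared exploratory, and that Section 13.3 claims no power for tumor tissue. All of that stands. A chance imbalance that resembles a drug effect is already within the 5% error rate, and stratification makes an unadjusted test somewhat conservative.

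A reader might infer that all six markers track invasion, so that the second-ranked secondary objective, tumor phosphorylated EGFR, loses a strong known predictor. The documents do not support this. The Section 2.3 statement concerns receptor overexpression and grade/stage, not phosphorylation. Ki-67 is tied to proliferation, let-7 to dedifferentiation and p-ERK to cancer progression in general. Section 9.1 also plans phosphorylated-to-total EGFR ratios, described for tumor against normal tissue, which would remove a difference due to receptor amount alone.

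A reader might also infer a bias, or a routine 17% risk of serious imbalance. Neither holds: randomization prevents systematic bias, and 17% ignores stratification by planned surgery. Section 2.1 says that muscle-invasive disease generally goes to cystectomy.

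Stratification does not fully answer the point, however. The tests ignore the stratum, so the spread stays in the error term. Planned surgery need not separate T1 from Ta tumors, and balance at randomization does not guarantee balance among those who yield tumor tissue.

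The covariate is imperfect. It is a clinical impression, invasive is not defined (Section 2.1 classes T1 as superficial although it enters the lamina propria), entry on imaging alone is allowed, and the Schedule of Events has no row for it. With no imputation (Section 13.6), a missing value could drop a participant. These points reduce the gain and call for a fallback.

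Pre-to-post change gives within-patient control only where paired tissue exists. The normal-minus-neoplastic difference does not remove the effect, since invasion would mainly alter the tumor value.

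**Conclusion.** The point holds as a modest loss of precision in exploratory secondary comparisons. A baseline assessment required by Section 7.2, and a stratum fixed at randomization, go unused where the protocol gives reason to expect a relation: directly for E-cadherin, less directly for total EGFR and p53. For the other markers, a gain is possible but undocumented.

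Adjustment cuts the standard error by about 1% to 18%, assuming an invasive share of 10% to 30% and a difference of 0.5 to 1.5 within-type SD. At 30% invasive, a gap of 20 points or more in invasive share arises in about 17% to 18% of trials if planned surgery is uninformative, and in about 12% or 4% if cystectomy is planned for 50% or 80% of invasive tumors. The documents give neither the trial's invasive share nor the marker differences, so these are ranges, not estimates.

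**What to change.** - **Model.** In Section 13.5, prespecify for the continuous neoplastic-tissue markers and the normal-minus-neoplastic difference a linear model on the transformed or rank scale, or a stratified rank-sum test, with arm and the pre-dose invasive/non-invasive assessment.
- **Data.** Define the assessment and record it on the CRF. Use the planned-surgery stratum where it is missing, so that no participant is dropped. Report invasive status by arm among those with tumor tissue.
- **Sensitivity.** Keep the unadjusted test as a sensitivity analysis.
- **What not to use.** Do not adjust for pathological stage at surgery. It follows dosing and may be affected by it; Section 2.3 describes down-staging at cystectomy after neoadjuvant erlotinib.

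The cost is some SAP wording, a CRF item and one degree of freedom. The gain falls to the low end, about break-even, if the clinical assessment misclassifies invasion or the marker does not track it.

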International Prostate Symptom Score (I-PSS). Hyperplasia and inflammation are directly or indirectly linked to carcinogenesis. Thusly, we are interested in prostatic hyperplasia. Little is known about the role of EGFR in benign prostatic hyperplasia. Recently, fibrosis has been implicated as a major player in benign prostatic hyperplasia (Ma 2012, Macoska 2012, Rodriguez-Nieves 2013). Fibrosis of the urinary tract has largely been assessed in kidney disease (Chen 2012) and EGFR appears to be a key mediator of fibrosis. However, less is known about the role of EGFR in fibrosis of the prostate and BPH. Our unpublished findings have identified that when the EGFR ligand, TGF-alpha, is force expressed in mice, prostatic fibrosis and increased rates of lower urinary tract dysfunction ensue. Additionally, we have demonstrated that EGFR-phosphorylation promotes collagen type 1 expression in prostatic stromal cells grown in vitro and the EGFR inhibitor, erlotinib, decreased prostatic collagen gene expression in these cells. These preliminary findings suggest that EGFR inhibitors may positively affect lower urinary tract symptoms.

As a part of our preliminary study of erlotinib in participants at risk of bladder neoplasia, we would like to perform an exploratory assessment of men randomized onto the study whether urination symptoms alter while on study. A well documented survey (IPSS) of urination symptoms which correlates with prostatic hyperplasia in men will be filled out by men at baseline and end of study.

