13.2 Randomization and Stratification

Randomization will be in a ratio of 1:2 in Placebo (4 tablets): erlotinib (4 tablets) by mouth once weekly, based on a permuted block of size 3 with stratification by planned use of agents that significantly decrease Erlotinib bioavailability (tobacco, protein pump inhibitors) and by planned surgery (TURBT vs. cystectomy). The decision was made not to stratify by site to avoid problems with sparse data. After random permutation of numbers from 1 to 3 in each block, incoming subjects in sequence will be randomized to treatment corresponding to the permuted numbers in sequence according to the following: placebo for number 1, and erlotinib for numbers 2 and 3. This process will be repeated after every 3 subjects.

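### No secondary analysis uses the baseline value: the I-PSS has no named between-arm comparison, and paired tissue is tested on unadjusted change

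*Combined protocol and SAP*

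**What the plan says.** **Paired tissue.** Section 13.5 compares tissue markers between arms at the time of surgery and adds that "for those with available paired tissue samples we will examine pre to post change". Continuous markers get a two-sample t-test, transformed if necessary, or a Wilcoxon rank-sum test. Section 8.2 explains that only some participants will have earlier tissue, from an initial diagnostic cystoscopy or an initial TURBT. It does not say how many.

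**I-PSS.** Section 8.2 says the questionnaire "will be filled out by men at baseline and end of study", and the Section 7.1 schedule places it at baseline and at the surgery visit. Section 1.2 lists it as an exploratory objective. Section 13.5 does not name it. The only sentence that reaches it says that "all measurements and changes in measurements of interest will be summarized by treatment arm", with descriptive statistics.

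**Covariates.** The only analysis in the plan that accounts for covariates is the supporting analysis of the primary endpoint in Section 13.4 (dose received, smoking, proton pump inhibitor use). No secondary analysis uses a baseline value as a covariate.

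**The concern.** The trial collects a pre-treatment I-PSS in every man and will hold pre-treatment tissue for some participants, but the plan does not use either value to sharpen a between-arm comparison.

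For paired tissue, the planned test subtracts baseline in full. When the correlation between the two measurements is low, subtraction adds noise. Low correlation is plausible here because the earlier block comes from a separate procedure, and exclusion 4.2.1 permits intravesical therapy in the interval before study surgery.

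For the I-PSS, the plan leaves the comparison open. End value, change or adjusted value could be chosen after the data are seen, and the change summaries that Section 13.5 calls for make raw change the natural default. What is at stake is precision in small 1:2 groups, and an estimate that moves with whatever baseline difference chance produces.

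**Working it through.** **1. The plan's own figure.** Section 13.3 uses a "two-tailed two-sample t-test of the difference between the two groups at a significance level of 0.05" and an effect of 1 SD, and states that "with power 0.85, the trial requires an effective sample size of 14 in the placebo arm and 28 in the erlotinib arm". The normal approximation gives n = 14 and 28 (power 0.863). The noncentral t gives power 0.846 at 14 v 28, which rounds to the stated 0.85. Allowing 5% dropout gives 15 and 30. The figure reproduces and is not in dispute. It concerns the primary endpoint only; no figure is given for the I-PSS or for paired tissue.

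**2. Inputs.**
- Men: Section 4.3 reports 76% male patients at the consortium sites, taken here to apply to this trial. 0.76 × 14 = 10.6 and 0.76 × 28 = 21.3, so 11 v 21, N = 32.
- Correlation rho between baseline and end of study: not in the documents; range 0.3 to 0.9.
- I-PSS effect: not in the documents; 0.5 SD for illustration.
- Number of tissue pairs: not in the documents; 9, 12 and 15 for illustration.

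**3. Variances**, in units of the single-visit variance, equal at both visits:
- change: 2(1−rho)
- adjusted, large sample: 1−rho²
- ratio of change to adjusted: 2/(1+rho), which is 1.54 at rho 0.3, 1.33 at 0.5, 1.18 at 0.7 and 1.05 at 0.9
- end value alone: 1, so below rho 0.5 change is noisier than ignoring baseline (1.4 v 1.0 at rho 0.3)
- adjusted, small sample: (1−rho²)(1 + 1/(N−4)), the extra factor being the cost of estimating the slope

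**4. I-PSS power**, two-sided 5%, noncentral t. Noncentrality is d√(n1·n2/(n1+n2))/√V, with N−2 df for change and N−3 for adjusted. At 11 v 21 and d = 0.5 the numerator is 0.5 × √(231/32) = 1.343. At rho 0.5, V is 1 for change and 0.75 × (1 + 1/28) = 0.777 for adjusted, so the noncentralities are 1.343 and 1.524.

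| rho | change | adjusted |
|---|---|---|
| 0.3 | 20% | 27% |
| 0.5 | 26% | 31% |
| 0.7 | 39% | 43% |
| 0.8 | 54% | 57% |
| 0.9 | 83% | 83% |

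**5. Chance imbalance.** The SE of the baseline difference at 11 v 21 is √(1/11 + 1/21) = 0.37 SD. A change comparison shifts by −(1−rho) times the observed difference. For a one-SE imbalance that is 0.26 SD at rho 0.3, 0.19 at 0.5 and 0.11 at 0.7. In simulation (20,000 runs per case, true effect 1 SD) the slope of the estimate on the imbalance was −0.50 at rho 0.5 and −0.29 at rho 0.7 for change, and about 0 for the adjusted model. Both methods averaged the true effect.

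**6. Paired tissue power**, 1 SD effect, slope cost included (change → adjusted):

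| rho | 3 v 6 | 4 v 8 | 5 v 10 |
|---|---|---|---|
| 0.3 | 18% → 21% | 24% → 30% | 30% → 39% |
| 0.5 | 23% → 24% | 32% → 36% | 39% → 46% |
| 0.7 | 35% → 33% | 48% → 49% | 59% → 61% |
| 0.8 | 49% → 44% | 64% → 63% | 76% → 76% |
| 0.9 | 77% → 70% | 91% → 88% | 97% → 96% |

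Adjustment has the smaller variance only while rho is below 2/(1 + 1/(N−4)) − 1. That is 0.93 at N = 32, 0.83 at N = 15, 0.78 at N = 12 and 0.67 at N = 9.

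**The case against.** **The I-PSS change test is not in the plan.** A reader might infer that Section 13.5 tests raw I-PSS change. It does not: it calls for summaries of values and of changes, and states no between-arm test. The power table therefore compares adjustment with the likely default, not with a planned test. This stands, and it makes the I-PSS point one of an unspecified analysis.

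**I-PSS correlation may be high.** Appendix C asks about the past month, and the second form is completed at surgery on about day 15-16. Its recall period therefore reaches back before the first dose and may overlap the baseline period. No correlation is given, but at 0.8 the gain is about 3 points and at 0.9 it is almost nil. This limits the benefit but does not turn it into a loss at any correlation in the table.

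**Adjustment is not always better.** The claim that its variance is never larger is a large-sample result. With a handful of tissue pairs and a high correlation, change is as good or better. This stands and rules out an unconditional rule for tissue.

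**Change is not biased.** A reader might infer that baseline imbalance biases the planned comparison. Under randomization it does not on average; the shift is conditional on the imbalance that happens to occur.

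**The stakes are small.** The I-PSS is exploratory, paired change supplements the surgery-time comparison, and Section 13.6 calls the study exploratory. This also stands.

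**Conclusion.** The point holds as a minor improvement. Section 13.5 makes no use of baseline as a covariate, leaves the I-PSS comparison between arms unnamed, and tests paired tissue on unadjusted change.

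For the I-PSS, baseline adjustment adds about 7 power points at rho 0.3, 6 at 0.5, 4 at 0.7 and 3 at 0.8, calculated before rounding. It also removes the dependence on chance baseline differences. This rests on assumed values for rho and the 0.5 SD effect, and on the 76% male share applying here. For paired tissue it is a trade-off that depends on the number of pairs, which the plan does not give.

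Nor are these the only measures with a pre-treatment value, as a reader might suppose: Section 7.1 also schedules baseline pharmacokinetic blood and safety laboratory tests. Nothing here touches the primary analysis or the sample size.

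**What to change.** In Section 13.5:

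- **I-PSS.** Name the between-arm analysis as a linear model, in men, of the end-of-study total score on arm and baseline score. Report the adjusted difference with a 95% confidence interval, and keep raw changes by arm as description only.
- **Paired tissue.** Use the same model for continuous markers only if the number of pairs reaches a prespecified minimum of about 15, where the break-even correlation is about 0.8. Otherwise keep the planned change analysis.

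The data are already being collected, so the practical cost is wording. The statistical cost is one degree of freedom and a variance factor of about 1 + 1/(N−4): 1.04 with 32 men and 1.09 with 15 pairs. Fixing the model in advance also closes off a later choice between end value, change and adjusted value.
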